Social incentives or those influences that impact individuals to adjust their behaviors based on social ties and connections have been demonstrated in retrospective studies to influence behavior but have not been well examined prospectively. Insights from behavioral economics can be used to design gamification interventions to enhance social incentives such as the support, competition, or collaboration but the optimal design to increase physical activity is unknown. This study will use behavioral economics frameworks to design and test a social incentive-based gamification intervention with and without financial incentives to increase physical activity among overweight and obese veterans. We will test whether this intervention can be conducted remotely, thereby reducing participant burden of coming in for an in-person visit and creating a more scalable intervention design. Specifically, we will test the ability of using wearable devices with social and financial incentive-based interventions to augment physical activity as measured by change in mean daily step counts which will be tracked by a wearable activity tracker.

Section 4: Objectives Section

4.1. Describe the study's purpose, specific aims, or objectives.

The objective of this study is to use a randomized, controlled trial to test the effectiveness using a remotely-monitored social incentive-based gamification intervention with and without financial incentives to increase physical activity among overweight and obese veterans. All participants will use wearable devices to establish a baseline step count and monitor their physical activity during the study.

Primary outcome: The primary outcome is change in mean daily steps from baseline to the weeks 5 to 12 of the intervention period (which excludes the 4-week ramp-up phase).

Secondary outcomes: Secondary outcomes include change in mean daily steps from baseline to the 8-week follow-up period, Proportion of participant-days achieving step goals during the intervention and follow-up periods.

Exploratory outcomes: We will explore how participant characteristics and behaviors are associated with strong or poor physical activity performance.

4.2. **State the hypotheses to be tested.**

Hypothesis: The combination of social and financial incentives will lead to greatest increase in mean step counts from baseline.

Section 5: Study Procedures

5.1. **Study Design**

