5.1.1. **Describe in detail the experimental design, i.e. from recruitment procedures to study closure.**

Design: This is a three-arm randomized, controlled trial with a 12-week intervention period and 8-week follow-up period. The study will be conducted using Way to Health (WTH), a research information technology platform at the University of Pennsylvania that has been used previously at the CMCVAMC for a behavioral study.

Study duration: This study is anticipated to take up to 2 years to complete and includes a 12-week intervention period and 8-week follow-up period.

Target population: Veterans, age 18 years or older, who received care at the CMCVAMC and have a body mass index of 25 or greater.

Accrual: This study has been powered for two phases of hypothesis testing. In the first phase, we will compare each of the two intervention arms to control. We estimate that a sample of 180 participants allocated in a 1:1:1 distribution, will ensure at least 80% power to detect a 900-step difference between each intervention arm and control, with a standard deviation of 1500 steps. This calculation assumes a 10% missing data rate and a conservative Bonferroni adjustment of the type I error rate with a 2-sided alpha of 0.025. In the second phase, we will compare successful intervention arms to each other. We expect that the magnitude of difference between intervention arms will be less than that of successful intervention arms compared to control. For this second phase of analyses will use a conservative Bonferroni adjustment of the type I error rate with a 2-sided alpha of 0.017 to adjust for up to 3 comparisons. In 2012, more than 57,500 veterans enrolled for care at CMCVAMC and comprised nearly 463,000 visits. Since 70% of veterans are overweight or obese, nearly 40,000 veterans may be eligible for this study. Based on this data and prior studies, we estimate that we can fill the study within 6 months. We will plan to oversample women and minorities in the recruitment process.

Interventions:

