5.4.5. **Inclusion/Exclusion Criteria: Describe the criteria that determine who will be included in or excluded from the study.**

5.4.5.1. **Inclusion Criteria**

1) Age 18 years or older; 2) interest in participating in a 20-week study using wearable devices to track step counts and increase physical activity; 3) body mass index of 25 or greater; 4) Smartphone or tablet compatible with application for the wearable activity tracking device.

5.4.5.2. **Exclusion Criteria**

1) Conditions that would make participation infeasible such as inability to provide informed consent, illiteracy or inability to speak, read, and write English; 2) conditions that would make participation unsafe such as pregnancy or being told by a physician not to exercise; 3) already enrolled in another study targeting physical activity; 4) any other medical conditions or reasons he or she is unable to participate in a physical activity study for 20 weeks.

5.5. **Withdrawal of Subjects**

5.5.1. **Describe how a subject can withdraw from the study.**
Subjects may withdraw at any point by informing the study team either by written mail or by phone.

5.5.2. **Describe any anticipated circumstances under which subjects will be withdrawn from the research without their consent.**
None.

5.5.3. **Describe the consequences of a subject's decision to withdraw from the research and the procedures for orderly termination of participation by the subject (e.g., the subject contacting the investigator for an end-of-study visit).**
Patients choosing to withdraw early in the study will not receive the total compensation as described above. Patients are free to, at any time, contact the study team to be removed from the study.

5.6. **Potential Risk/Benefit Analysis**

5.6.1. **Potential Study Risks**

5.6.1.1. **Describe and assess all of the following risks that may be associated with the research:**

5.6.1.2. **Physical**

To minimize the chance for serious and unexpected adverse events, study participants will be screened through exclusion criteria for any health conditions that may be exacerbated by participating in a physical activity study. The program will use a gradual increase in physical activity during the first month that should pose little health risk to participants. Participants are given guidance on when to seek medical attention and a reporting protocol is in place to capture any changes in symptoms with physical activity.

5.6.1.3. **Psychological:** Not applicable.

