### **2. Missing Data**

- a. For outcome variables (Daily Steps) identify missing values at weeks 1-12, 1-4, 5-12, and 13-20
- b. For Steps separately list values that are missing from values that are <1000

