### **4. Imputation plan**

- a. Change in mean daily steps
  - i. Model driven approach to run 5 imputations for any missing values or values < 1000 steps
  - ii. Covariates include: study arm, week of study, calendar month, baseline step count, age, gender, race/ethnicity, education, marital status, annual household income, military service period, and BMI

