### **6. Adjusted changes in outcome measures (imputed model is primary; non-imputed is secondary)**

- a. Use generalized linear mixed models (GLIMMIX) with identity link for mean change in daily steps during weeks 5-12 and weeks 13-20.
  - i. Adjusted for baseline steps, calendar month, study arm, participant random effect
- b. Use generalized linear mixed models (GLIMMIX) with logit link (logistic model) for proportion of days achieving step goal during weeks 5-12 and weeks 13-20
  - i. Adjusted for baseline steps, calendar month, study arm, participant random effect
  - ii. Use 1000 bootstrapped samples to find adjusted changes in percentage points with 95% confidence intervals for proportion of days achieving step goals

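### The imputation plan names no arm-by-period term; fitted as one main-effects model, it pulls each period's primary estimate slightly toward a pooled arm effect

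*SAP*

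**What the plan says.** SAP 4.a.i sets the method: "Model driven approach to run 5 imputations for any missing values or values < 1000 steps". SAP 4.a.ii gives the predictors: "Covariates include: study arm, week of study, calendar month, baseline step count", followed by demographic and service variables and BMI. Arm and week appear as separate items. No interaction is named, and nothing says whether one model covers all 20 weeks or each period is imputed separately. Protocol 9.2 adds only that missing days and days below 1000 steps will be imputed.

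The heading of SAP section 6 fixes the status of the result: "imputed model is primary; non-imputed is secondary". SAP 6.a then models "mean change in daily steps during weeks 5-12 and weeks 13-20". Protocol 4.1 makes the first window the primary outcome and the second a secondary outcome.

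The plan treats the 20 weeks as distinct phases. Protocol 5.1.1 states "This is a three-arm randomized, controlled trial with a 12-week intervention period and 8-week follow-up period". Protocol 4.1 defines the primary window as one "which excludes the 4-week ramp-up phase", and Protocol 5.6.1.2 says "The program will use a gradual increase in physical activity during the first month". SAP 2.a asks the analyst to "identify missing values at weeks 1-12, 1-4, 5-12, and 13-20", but that is a tabulation of missing days and not a rule for imputing them.

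**The concern.** The analysis lets the arm effect differ between weeks 5-12 and weeks 13-20. An imputation model with only main effects for arm and week does not. Week and calendar month move all arms up or down together, so the difference between arms on an imputed day is the same in week 2, week 10 and week 18. The imputation model is then more restrictive than the analysis it feeds, and the imputed days carry that restriction into the primary result.

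Two readings are at stake. The weeks 5-12 estimate is the primary outcome, and under plausible patterns it would be diluted. The weeks 13-20 estimate shows whether any effect lasts, and some of the intervention-period effect would be mixed into it.

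**Working it through.** **Inputs from the documents.** Protocol 9.1: 180 participants allocated 1:1:1, a 900-step difference, SD 1500, two-sided alpha 0.025, 10% missing data, at least 80% power. Periods: weeks 1-4 (4 weeks), 5-12 (8 weeks), 13-20 (8 weeks).

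**Assumptions.** The documents give no effect by period. I take 900 steps in weeks 5-12 and vary the ramp-up effect r and the follow-up effect d. I take 10% of days as imputed in every period; Protocol 9.1 does not say that its 10% is a share of days. Days are missing at random.

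**The plan's own figure.** n per arm = 2 × (2.241 + 0.842)² × (1500/900)² = 52.8, so 53. Divided by 0.90 this is 59 per arm, or 177 in total, which agrees with 180. With 54 evaluable per arm, SE = 1500 × √(2/54) = 289 and power = Φ(900/288.7 − 2.241) = 81.0%.

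**Shift from a pooled arm effect.** With an equal imputed share m in each period:

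- pooled = (4r + 8×900 + 8d)/20
- estimate in a period = (1 − m) × true + m × pooled, so shift = m × (pooled − true)

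Worked example, r = 450, d = 0, m = 0.10: pooled = (1800 + 7200 + 0)/20 = 450. Weeks 5-12 = 0.9×900 + 0.1×450 = 855. Weeks 13-20 = 0 + 45 = 45.

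| r | d | pooled | shift, weeks 5-12 | shift, weeks 13-20 |
|---|---|---|---|---|
| 450 | 0 | 450 | -45 | +45 |
| 900 | 0 | 540 | -36 | +54 |
| 450 | 450 | 630 | -27 | +18 |
| 900 | 450 | 720 | -18 | +27 |
| 450 | 800 | 770 | -13 | -3 |
| 900 | 800 | 860 | -4 | +6 |
| 450 | 1000 | 850 | -5 | -15 |
| 900 | 1000 | 940 | +4 | -6 |
| 900 | 900 | 900 | 0 | 0 |

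The largest shifts in the table are 45/289 = 0.16 SE at weeks 5-12 and 54/289 = 0.19 SE at weeks 13-20. An extreme ramp-up effect of 0 with d = 0 gives pooled = 360, with shifts of -54 (0.19 SE) and +36.

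**Direction.** Weeks 13-20 is pulled up if d < (4r + 7200)/12, which is 600, 750 or 900 for r = 0, 450 or 900. Weeks 5-12 is pulled down if d < (10800 − 4r)/8, which is 1350, 1125 or 900.

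**Power for the primary comparison.** Power = Φ(estimate/SE − 2.241), with SE = 274 for 60 per arm:

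| Weeks 5-12 estimate | 60 per arm | 54 per arm |
|---|---|---|
| 900 (no shift) | 85.2% | 81.0% |
| 882 | 83.6% | 79.2% |
| 873 | 82.8% | 78.3% |
| 864 | 82.0% | 77.4% |
| 855 | 81.1% | 76.4% |

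If everyone contributes and single days are missing, the 60-per-arm column applies. If whole participants are lost as well, the 54-per-arm column does.

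**Sensitivity to the imputed share.** The shift is proportional to m when m is equal across periods: 5% halves it and 20% doubles it. If 10% of days are imputed through week 12 and 30% afterwards, the pooled effect is weighted by observed days. For 450/900/0 it is (3.6×450 + 7.2×900)/16.4 = 494, and weeks 13-20 moves by 0.3×494 = +148.

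**Simulation check.** Setup: two arms of 60, 140 days, 10% of days missing at random, between-person SD 1500, assumed day-to-day SD 2500, a person effect in the imputation, 5 imputations, 600 trials per pattern. Main-effects minus arm-by-period imputation, at weeks 5-12 / weeks 13-20, gave -45 / +45 for 450/900/0, -28 / +19 for 450/900/450 and 0 / 0 for 900/900/900 (simulation SE 0.5 to 0.6). In a smaller simulation of 450/900/450, the shift against complete data was -28 / +20 without a person effect and -29 / +16 with one. In the unequal-effect patterns, an arm-by-period term brought the shift close to zero.

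**The case against.** The strongest reply is that no error is shown. SAP 4.a.ii is a list of variables in a terse plan and not a model formula. An interaction or by-period imputation is not ruled out, and the bias also needs arm effects that differ by period, which the documents do not state. This stands, and it is why the point is conditional.

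One can add that SAP 6.a.i also lists study arm with no period term, yet is read as giving separate estimates. But SAP 6.a names the two windows, and Protocol 4.1 defines them as separate outcomes. Nothing comparable exists for the imputation. The weeks 1-20 summary in SAP 5.a fits a single imputation over all weeks, though stacked period-wise imputations would fit too.

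It is also fair that the lower power figures combine lost participants with imputed days. With 60 per arm, power stays above 80% at every estimate tabulated, and even the extreme case (846 steps) gives 80.2%.

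Finally, the planned non-imputed analysis contains no imputed days, so this mechanism cannot act on it. That makes it a useful comparison. But it is secondary, it could differ from the imputed result for other reasons, and it does not repair the primary estimate.

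**Conclusion.** The point holds as a conditional, minor one. Fitting the listed covariates as main effects in a single model over weeks 1-20 biases the imputed, primary analysis whenever the arm effect differs across ramp-up, intervention and follow-up. The three-phase design gives reason to expect that it may.

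At 10% of days imputed, with a ramp-up effect of 450 to 900 steps, the shift is at most 45 steps at weeks 5-12 and 54 at weeks 13-20, under 0.2 SE. It is under 0.1 SE if the effect halves after week 12. It is zero if the effect is constant, its sign depends on the true period effects, and it grows with the share of days imputed, which includes days below 1000 steps. All period effects other than 900 are assumptions. Nothing here implies an excess of false positives.

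**What to change.** In SAP 4.a.ii, add an arm-by-study-period term to the imputation model, with periods weeks 1-4, 5-12 and 13-20. Alternatively, state that imputation is run separately in each of these periods. If either was always intended, the line simply records it.

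The cost is one sentence, a few extra parameters and slightly less precise imputations. No additional data are needed.

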### **5. Unadjusted: Estimate Mean and SD for outcome measures (using imputed data)**

- a. Daily steps during baseline, weeks 5-12, weeks 13-20 and weeks 1-20
  - i. Graph monthly trends
- b. Proportion of days achieving step goal during 5-12 weeks and weeks 13-20

### **6. Adjusted changes in outcome measures (imputed model is primary; non-imputed is secondary)**

- a. Use generalized linear mixed models (GLIMMIX) with identity link for mean change in daily steps during weeks 5-12 and weeks 13-20.
  - i. Adjusted for baseline steps, calendar month, study arm, participant random effect
- b. Use generalized linear mixed models (GLIMMIX) with logit link (logistic model) for proportion of days achieving step goal during weeks 5-12 and weeks 13-20
  - i. Adjusted for baseline steps, calendar month, study arm, participant random effect
  - ii. Use 1000 bootstrapped samples to find adjusted changes in percentage points with 95% confidence intervals for proportion of days achieving step goals

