In order to minimize cost, time and travel for Veterans and to make study the least burdensome as possible, recruitment and enrollment will be completed remotely. Veterans will be asked to verify their identity using their name and age. Participants will be enrolled remotely using a standardized eligibility survey which will be conducted over the phone. Once deemed eligible and oral consent is obtained, participants will be asked to complete a telephone survey to obtain demographic data, activity data and information on use of technology. Participants will be told to wear the activity tracking device during day and night to get accustomed to it during a 2-week run-in period. Data collected from this time will be used to estimate a baseline step count using methods from prior work by using data from the second week (days 8 to 14), ignoring values less than 1000 steps (since evidence suggests these values are unlikely to represent actual activity). Participants without at least 4 days of data will be called to inquire if there are any issues with using the device and the period will be extended until at least 4 days of data are available to estimate a baseline step count.

Participants that have been confirmed by the study team to have an appropriate baseline step count will be called and asked to select a step goal increase as follows:

Goal Setting: Each participant will be asked to choose a step goal increase that is between 33% and 50% higher than their baseline (each step goal will be rounded up to the nearest hundred). A participant may also select to choose another goal as long as it is at least 1500 steps greater than his or her baseline.

Randomization: Participants are considered ready to be randomized once they have completed all surveys, established a baseline step count, and selected a step goal increase. Participants will be stratified on baseline step count (less than 5000 steps, 5001 to 7500 steps, or more than 7500 steps). Participants will then be randomly assigned within their strata in blocks of three. Participants in all arms will be asked to complete end of study surveys at 20 weeks on their experience in the study. The interventions within each arm are as follows:

Arm 1: Control

Participants in this arm will receive no other interventions during the 20-study.

Arm 2: Social incentive-based gamification intervention

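### The goal-attainment model in SAP 6.b.i leaves out the step goal that each participant chose before randomization; adding it costs nothing and may improve precision, by an amount the documents cannot fix

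*SAP*

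**What the plan says.** **Endpoint.** Protocol 4.1 lists among the secondary outcomes "Proportion of participant-days achieving step goals during the intervention and follow-up periods".

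**Goal.** Protocol 5.1.1 (Goal Setting) gives a standard option: "Each participant will be asked to choose a step goal increase that is between 33% and 50% higher than their baseline", rounded up to the next hundred. It then gives an alternative: "A participant may also select to choose another goal as long as it is at least 1500 steps greater than his or her baseline". No upper limit is stated.

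**Timing.** Under Randomization in the same section, a participant is ready only after having "established a baseline step count, and selected a step goal increase". This applies to all three arms. The strata use baseline step count alone.

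**Model.** SAP 6.b specifies a mixed model with "logit link (logistic model) for proportion of days achieving step goal during weeks 5-12 and weeks 13-20". Its covariate line, 6.b.i, reads "Adjusted for baseline steps, calendar month, study arm, participant random effect", which repeats 6.a.i, the line for the step-count model. SAP 6.b.ii then takes adjusted percentage-point changes from 1000 bootstrap samples. The goal is not among the imputation covariates in SAP 4 either. Protocol 9.2 says only that logistic models will be used for this endpoint.

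**The concern.** For mean daily steps, the goal plays no part in defining the outcome. For goal attainment it is the threshold. Two people with the same baseline and the same daily steps can have quite different proportions of successful days only because one picked a harder goal. The SAP nevertheless uses one covariate line for both outcomes.

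The goal is set before allocation, so treatment cannot affect it and it is a legitimate baseline covariate. When it is left out, differences in goal difficulty that baseline steps do not explain stay in the between-participant variance. What is at stake is the width of the confidence intervals for this endpoint in weeks 5-12 and 13-20, and the chance to adjust for an accidental imbalance in goal difficulty with about 60 participants per arm.

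**Working it through.** **1. The plan's own figure.** The documents give a sample size for mean steps only (Protocol 9.1: difference 900, SD 1500, two-sided alpha 0.025, 80% power, 10% missing).

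n per arm = 2 × (1500/900)² × (2.241 + 0.842)² = 52.8, so 53. Then 53/0.90 = 58.9, so 59 per arm and 177 in total, against 180 stated. The figure reproduces. There is no power or precision figure for goal attainment to check.

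**2. How far goals can differ at one baseline** (rules in Protocol 5.1.1)

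| Baseline | Goal at +33% | Goal at +50% | Lowest alternative goal (+1500) |
|---|---|---|---|
| 3000 | 4000 | 4500 | 4500 |
| 5000 | 6700 | 7500 | 6500 |
| 7500 | 10000 | 11300 | 9000 |
| 10000 | 13300 | 15000 | 11500 |

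The alternative lies below the 33% goal only when baseline exceeds 1500/0.33 = 4545.

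**3. Share of between-person variation in distance to goal that comes from the goal.** Share = V/(V + 1500²), where V = width²/12 if goals are uniform over the range (an assumption), and 1500 is the protocol's SD.

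- 33-50% band, width 0.17 × baseline. At 5000: 850²/12 = 60208, share 2.6%. At 7500: 5.7%. At 10000: 9.7%.
- From +1500 to +50%. At 5000, width 1000: 3.6%. At 7500, width 2250: 15.8%. At 10000, width 3500: 31.2%.

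**4. What this does to attainment.** Assume a mean rise of 900 steps, a between-person SD of 1500 and a day-to-day SD of 2500 (the last is not in the documents). Expected attainment = 1 − Φ((increment − 900)/√(1500² + 2500²)), with denominator 2915.

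- Baseline 6000: 42% for +1500, 35% for +33% (goal 8000), 24% for +50% (goal 9000).
- Baseline 10000: 42%, 21% and 8%.

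**5. Effect on the arm contrast.** This simulation is a linear stand-in for the SAP model: each person's proportion of days at goal is regressed on arm and baseline, with and without the goal increment.

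Inputs from the documents: 54 evaluable per arm (60 × 0.90), 56 days (weeks 5-12), effect 900, SD of change 1500. Assumed inputs: baseline mean 6500 and SD 2500, floored at 2000; control change +300; day-to-day SD 2500; the distribution of goals. There were 2000 simulated trials per row. The range in the last column covers two ways of defining the correlation (overall, or given baseline).

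| Goal choices | Variance ratio, goal unrelated to true change | Variance cut | SE cut | Variance cut if goal increment correlates 0.3 with true change |
|---|---|---|---|---|
| All uniform in 33-50% | 0.976 | 2% | 1.2% | 0 to 1% |
| One fifth at +1500, rest in band | 0.867 | 13% | 7% | 1 to 5% |
| Equal thirds at +33%, +50%, +1500 | 0.821 | 18% | 9% | 5 to 8% |

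The SE cut is 1 − √ratio. The estimated arm difference was essentially unchanged by the extra covariate in every row. The worst ratio was 1.004, a loss of under 1%.

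A much wider spread of goals (everyone at 1500 plus an exponential amount with mean 1500, 60 per arm, day-to-day SD 2500 to 3500) gave variance cuts of 18% to 31%. That scenario abandons the standard band altogether and serves only as an outer case.

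**The case against.** The strongest reply is that this is an optional refinement to a secondary endpoint. Several parts of it stand.

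- The model does not rest on baseline steps alone. It also has calendar month, arm and a participant random effect. The random effect takes up goal-driven differences between people, so repeated days are handled properly. Randomization balances goals in expectation, and ordinary standard errors already allow for chance imbalance.
- Goals are set relative to baseline, so the baseline covariate already carries much of their variation. Within the standard band there is almost nothing left to gain.
- The documents do not say how many people took the alternative. Participants are asked to use the band; the other route is something they may choose.
- Independence between goal choice and later change favours the covariate. People who intend to walk more may set higher goals, and then most of the gain goes.
- The calculation is linear on per-person proportions, whereas the SAP uses a logit mixed model on days.
- A common covariate set for both outcomes is a legitimate prespecified choice.

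These points limit the size of the gain. They do not give a reason to leave out the variable that defines the endpoint, since including it cost at most a fraction of a percent in the cases tried.

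A further reply is that an added covariate changes what a logistic coefficient means. That is true of the conditional odds ratio. It matters much less for the percentage-point change of 6.b.ii, provided predictions are averaged over participants.

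**Conclusion.** The omission is real and its consequence is confined to precision. The variance reduction runs from about 2% (all goals in the band) to about 13-18% (a fifth to a third of participants at +1500). It is small or absent if higher goals go with larger true increases. These figures rest on the assumed baseline distribution, day-to-day SD, goal mix and linear stand-in; only the 900-step effect, the SD of 1500 and the 10% missing rate come from the plan.

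Two stronger readings are tempting and are not supported. A reader might infer that the arm comparison is biased or its type I error wrong; it is not, because the goal precedes randomization and the random effect absorbs the variation. A reader might also infer that the goal is a major known source of lost power. In the equal-thirds case the stand-in's power at alpha 0.025 did rise from about 60% to 69%, but that mix of goals is invented, and the figure is not the power of the planned test. The primary endpoint and the sample size are untouched.

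**What to change.** In SAP 6.b.i, add the goal increment (selected goal minus baseline steps, both fixed before randomization) as a fixed covariate, for weeks 5-12 and for weeks 13-20. In 6.b.ii, fit the same model in each of the 1000 bootstrap samples and average predictions over participants, so that the percentage-point difference remains the reported result. State this before goals or outcomes are examined by arm.

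The cost is one line in the SAP. The goal must already be held for every participant, because the endpoint cannot be derived without it. No further data or participants are needed, and 6.a stays as it is.
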